5.5.4.3 Rescue Medication Use

Blinded Phase:

The number of days that rescue medication (RM) was taken since the previous visit will be collected throughout the trial at scheduled visits and safety telephone calls.

To standardize between patients, the total number of days RM was taken will be calculated as the sum of all reported records within a period. Hence, the average number of days RM was taken per 28 days within a period will be calculated as follows:

$(\text{Total number of days RM was taken during the period} \div \text{Number of days in the period}) \times 28$

This will be calculated for both the baseline period and treatment period. The number of days in a period will be calculated as the number of days from the visit prior to the first recorded value in the period to the day of the last recorded value in the period. The baseline period refers to the period between Visit 2 and Visit 3. The treatment period refers to the period between Visit 3 and Visit 10.

The number of days RM was taken per 28 days will be summarized by period and treatment arm. The change from the baseline period will also be included.

The change from the baseline period to the treatment period will be analyzed using an ANCOVA approach. The model will include the baseline period and stratified age group as covariates and treatment arm as fixed factor.

The estimated least squares means, treatment difference, together with the 95% CIs and p-value will be presented.

Open-label Extension:

Descriptive summaries described above for the blinded phase will be repeated for the OLE period. The OLE period refers to the period between Visit B1 and the last available visit in the OLE phase.

5.5.4.4 Status Epilepticus

The number of episodes of status epilepticus will be collected daily via IVRS for the blinded phase and weekly via IVRS for the open-label extension.

The number of patients with status epilepticus will be presented for the baseline, treatment and OLE periods.

5.5.4.5 Subject/Caregiver Global Impression of Change in Seizure Duration

Blinded Phase:

The SGICSD and CGICSD comprise the following questions to be rated on a 3-point scale for each seizure type:

CGICSD:

- Since the patient started treatment, please assess the average duration of the patient's seizures (comparing their condition now to their condition before treatment) using the scale below.

SGICSD:

- Since you started treatment, please assess the average duration of your seizures (comparing your condition now to your condition before treatment) using the scale below.

The 3 possible responses are:

- Decrease in average duration.
- No change in average duration.
- Increase in average duration.

The patient/caregiver will be asked to assess the average duration of seizures at Visit 3 (prior to commencement of IMP) as a memory aid for assessment further visits.

Each response will be coded with a score from 1 to 3, where 1 = Decrease in average duration, and 3 = Increase in average duration.

For each seizure type, the SGICSD and CGICSD will be summarized separately by treatment arm.

It is anticipated that only a small percentage of patients will complete the subject version of the questionnaire. Hence, no analyses will be performed for the SGICSD.

A combined score will be used as the primary analysis for this endpoint. The combined score will be defined as follows:

- If both a CGICSD and SGICSD are completed then the CGICSD will be used.
- If only a CGICSD is completed then the CGICSD will be used.
- If only a SGICSD is completed then the SGICSD will be used.

Proportional odd modelling will be carried out by including treatment arm and age group as factors. The estimated odds ratio (GWP42003-P vs. placebo), 95% CI for the odds ratio, and the p-value testing the null hypothesis that the odds ratio is equal to 1, will be presented.

Since this analysis uses a combination of caregiver and subject ratings, a sensitivity analysis will be performed using only the CGICSD score and using the same analyses as above.

Open-label Extension:

Descriptive summaries described above for the blinded phase will be repeated for OLE visits.

5.5.4.6 Vineland Adaptive Behavior Scales, Second Edition

Blinded Phase:

The Vineland-II is an individually administered instrument for assessing adaptive behaviors and consists of 4 adaptive behavior domains and a maladaptive behavior domain. The details of each domain are presented in Table 5.

Table 5 Content Description of the Vineland-II

Domains and Subdomains	Number of Items	Age Range (Years)	Content
Adaptive Behavior Domains			
Communication Domain	99	≥ 0	
Receptive	20	≥ 0	How the individual listens and pays attention, and what he or she understands
Expressive	54	≥ 0	What the individual says, how he or she uses words and sentences to gather and provide information
Written	25	≥ 3	What the individual understands about how letters make words, and what he or she reads and writes
Daily Living Skills Domain	109	≥ 0	
Personal	41	≥ 0	How the individual eats, dresses and practices personal hygiene
Domestic	24	≥ 1	What household tasks the individual performs
Community	44	≥ 1	How the individual uses time, money, the telephone, the computer and job skills
Socialization Domain	99	≥ 0	
Interpersonal Relationships	38	≥ 0	How the individual interacts with others
Play and Leisure Time	31	≥ 0	How the individual plays and uses leisure time
Coping Skills	30	≥ 1	How the individual demonstrates responsibility and sensitivity to others
Motor Skills Domain	76	≥ 0 to <7	
Gross	40	≥ 0 to <7	How the individual uses arms and legs for movement and coordination
Fine	36	≥ 0 to <7	How the individual uses hands and fingers to manipulate objects
Maladaptive Behavior Domain			
Maladaptive Behavior Index	36	≥ 3	A composite of Internalizing, Externalizing, and Other types of undesirable behavior that may interfere with the individual's adaptive functioning
Internalizing (Section A)	11	≥ 3	
Externalizing (Section B)	10	≥ 3	
Other (Section C)	15	≥ 3	
Maladaptive Behavior Critical Items	14	≥ 3	More severe maladaptive behaviors that may provide clinically important information

For each subdomain, a raw score is calculated based on the responses to the individual items within the subdomain. For the maladaptive behavior index, the raw score is the sum of the 3 subdomain raw scores. Using the raw score and the patients' age the following are obtained:

- v-Scale Score: a type of standard score scale (standardized by age) to describe an individual's relative level of functioning. Ranging from a score of 1 to 24.
- 90% CI for the v-Scale Score: a range of scores that has a certain likelihood of including the individual's true score.

- Adaptive Level: a means to describe an individual's performance using terms that are nearly universal (Low, Moderately Low, Adequate, Moderately High, High).
 - For the maladaptive behavior index and maladaptive behavior subdomains the adaptive levels are: Average, Elevated or Clinically Significant.
- Age Equivalent: the age at which the raw score is average. Not applicable for the maladaptive behavior index and maladaptive behavior subdomains.

For each adaptive behavior domain, the sum of the v-scale scores of the subdomains is used along with the patients' age to obtain the following:

- Standard Score (standardized by age). Ranging from a score of 20 to 160.
- 90% CI for the domain standard score.
- Percentile Rank: the percentage of people whom the individual outperformed in his or her age group.
- Adaptive Level (Low, Moderately Low, Adequate, Moderately High, High).
- Stanine: whole number score ranging from 1 to 9 and representing a specific range of percentile ranks.

An adaptive behavior composite can then be obtained using the sum of the adaptive behavior domain standard scores (excluding the motor skills domain for patients ≥ 7 years of age). The same derived information as the adaptive behavior domain is obtained for the adaptive behavior composite.

For the maladaptive behavior index, all items within each section must be answered for a raw score to be calculated. If any of the items are missing then the maladaptive behavior index score will be missing.

For the adaptive behavior subdomains, the derivation of the raw score allows for up to 2 missing values or answers of "Don't Know" within the items used for scoring. If there are more than 2 missing values or answers of "Don't Know" then the raw score will not be calculated and the subdomain score, domain score and adaptive behavior composite score will be missing.

The adaptive levels corresponding to the v-scale scores and standard scores are presented in Table 6.

Table 6 Adaptive Levels by v-Scale Scores and Standard Scores

Adaptive Level	v-Scale Score for Subdomains and Maladaptive Behavior Index	Standard Score for Domains and Adaptive Behavior Composite
Adaptive Behavior Domains		
Low	1 to 9	20 to 70
Moderately Low	10 to 12	71 to 85
Adequate	13 to 17	86 to 114
Moderately High	18 to 20	115 to 129
High	21 to 24	130 to 160
Maladaptive Behavior Domain		
Clinically Significant	21 to 24	
Elevated	18 to 20	
Average	1 to 17	

The v-scale score from the 11 adaptive behavior subdomains, 3 maladaptive behavior subdomains and the maladaptive behavior index, and the standard score from the 4 adaptive behavior domains and the adaptive behavior composite, recorded at each visit, will be summarized, on a continuous scale, by treatment arm. The change from baseline will also be included.

The change from baseline to the end of treatment visit, for the 4 adaptive behavior domains, the adaptive behavior composite and the maladaptive behavior index only, will be analyzed using the same ANCOVA approach as specified in Section 5.5.3.2.4.

The adaptive level from the 11 adaptive behavior subdomains, 4 adaptive behavior domains, the adaptive behavior composite, the 3 maladaptive behavior subdomains and the maladaptive behavior index, recorded at each visit, will be summarized, on a categorical scale, by treatment arm.

The adaptive level from the 4 adaptive behavior domains, the adaptive behavior composite and the maladaptive behavior index only will be analyzed using ordinal logistic regression. Factors for treatment and age group will be included along with the baseline adaptive level as a covariate. The estimated odds ratios (GWP42003-P arms vs. placebo), 95% CI for the odds ratios, and the p-values testing the null hypothesis that the odds ratio is equal to 1, will be presented.

Each adaptive level for adaptive behavior will be coded with a score from 1 to 5, where 1 = Low, and 5 = High. Each adaptive level for the maladaptive behavior index will be coded with a score from 1 to 3, where 1 = Clinically Significant, and 3 = Average.

The individual responses within each domain will not be listed, only the derived information for each subdomain and domain will be listed.

Open-label Extension:

Descriptive summaries described above for the blinded phase will be repeated for OLE visits.

5.5.4.7 Wechsler Tests

Blinded Phase:

The Wechsler tests are age specific and will only be administered at a sub-group of centers that have the expertise to conduct the assessments. The age of the patient at entry is used when choosing the items to be administered. The following Wechsler Subtests will be used:

Age 2–6:

- Wechsler Preschool and Primary Scale of Intelligence – Fourth Edition (WPPSI-4) Vocabulary and Matrix Reasoning

Age 6–Adult:

- Wechsler Abbreviated Scale of Intelligence – Second Edition (WASI-2) Vocabulary and Matrix Reasoning
- Wechsler Intelligence Scale for Children – Fourth Edition (WISC-4) and Wechsler Adult Intelligence Scale - Fourth Edition (WAIS-4) Digit Span and Coding.

The T scores (Vocabulary and Matrix Reasoning), scaled scores (Coding) and forward, backward, longest forward and longest backward scores (Digit Span) will be summarized by visit including the change from baseline.

The change from baseline will be analyzed using an ANCOVA approach. The model will include baseline and stratified age group as covariates and treatment arm as fixed factor.

The estimated least squares means, treatment difference, together with the 95% CIs and p-value will be presented.

Open-label Extension:

Descriptive summaries described above for the blinded phase will be repeated for OLE visits.

5.5.4.8 Achenbach Child Behavior Checklists and Adult Behavior Checklist

Blinded Phase:

The Achenbach CBCL is a caregiver questionnaire assessing both behavioral and emotional symptoms in children. Depending on the patients' age, 1 of 2 versions of the Achenbach CBCL is used. The CBCL/1½-5 is used for children 18 months old to 5 years and 11 months old. For patients ≥6 and ≤17 years old the CBCL/6-18 is used. An adult version of the checklist, the Achenbach ABCL (ABCL/18-59), is used for patients ≥18 and ≤59 years old.

The CBCL/1½-5 comprises of 100 items, the CBCL/6-18 comprises of 113 items and the ABCL/18-59 comprises of 123 items. Response options are 0=not true; 1=somewhat or sometimes true; 2=very true or often true. Similar items are grouped and summed to produce syndrome scale scores, which are further grouped into problem scales as specified in Table 7. Other scales for CBCL/6-18 and ABCL/18-59 are also derived.

Derivation instructions for the Achenbach scales are given in Appendix 5. For each questionnaire, the individual item responses will not be listed, only the raw scores for the scales given in Table 7 and Table 8 will be listed. For the Achenbach CBCL/1½-5, no scoring will be performed for the language development survey. For the Achenbach ABCL/18-59, no scoring will be performed for the spouse/partner functioning scale or the tobacco, alcohol and drugs substance use scales.

The derived raw scores for the syndrome scales and problem scales as indicated in Table 7, recorded at each visit, will be summarized, on a continuous scale, by questionnaire version and treatment arm. The change from baseline will also be included.

The change from baseline to the end of treatment visit, for the internalizing, externalizing and total problems scales only, will be analyzed for each of the questionnaire versions using the same ANCOVA approach as specified in Section 5.5.3.2.4.

The raw scores for other scales as indicated in Table 8 will also be summarized.

Table 7 Achenbach CBCL and ABCL Syndrome and Problem Scales

Questionnaire Version	Problem Scales	Syndrome Scales
CBCL/1½-5	Internalizing	Emotionally Reactive
		Anxious/Depressed
		Somatic Complaints
		Withdrawn
	Externalizing	Attention Problems
		Aggressive Behavior
	Other	Other Problems
		Sleep Problems

	Total	
CBDL/6-18	Internalizing	Anxious/Depressed
		Withdrawn/Depressed
		Somatic Complaints
	Externalizing	Rule-breaking Behavior
		Aggressive Behavior
	Other	Social Problems
		Thought Problems
		Attention Problems
		Other Problems
	Total	
ABCL/18-59	Internalizing	Anxious/Depressed
		Withdrawn
		Somatic Complaints
	Externalizing	Aggressive Behavior
		Rule-breaking Behavior
		Intrusive
	Other	Thought Problems
		Attention Problems
		Other Problems
	Total	

Table 8 Achenbach CBCL and ABCL Other Scales

Questionnaire Version	Other Scales	Other Sub-Scales
CBDL/6-18	Total Competence	Activities
		Social
		School
ABCL/18-59	Friends	
	Critical Items	

Open-label Extension:

Descriptive summaries described above for the blinded phase will be repeated for OLE visits.

5.5.4.9 Social Communication Questionnaire

Blinded Phase:

The current version of the SCQ will be completed by the caregiver for all patients above the age of 4 years with a mental age of at least 2 years. The scale assesses behavior over the most recent three month period using 40 questions, each to be answered 'yes' or 'no'.

The answer to Item 1 'Is she/he now able to talk using short phrases or sentences?' is not scored and is instead used to determine which of the remaining items relating to abnormal language will contribute to the total score. If the answer to Item 1 is 'yes', then the six items relating to abnormal language will be used and the total score will range from 0 to 39 points from items 2 to 40. If the answer to Item 1 is 'no' then the six items relating to abnormal language will not be used and the total score will range from 0 to 33 points from items 8 to 40 only.

For Items 2, 9, 19 and 20–40, 'yes' will be assigned a score of 0 and 'no' a score of 1. For all other items, 'yes' will be assigned a score of 1 and 'no' a score of 0. The total score is calculated by taking the sum of the scores for each item.

In addition to the total score, the following domain scores will be derived:

- Reciprocal Social Interaction: Items 9, 10, 19, 26–33, 36, 37, 39 and 40.
- Communication: Items 2–6, 20–25, 34 and 35.
- Restricted, Repetitive and Stereotyped Patterns of Behavior: Items 7, 8 and 11–16.

The total score and domain scores will be summarized by visit including the change from baseline. The change from baseline for each score will be analyzed using an ANCOVA approach. The model will include baseline and stratified age group as covariates and treatment arm as fixed factor. Sex will also be included as a covariate in the model only if the p-value of the estimate is <0.05.

The estimated least squares means, treatment difference, together with the 95% CIs and p-value will be presented.

The individual responses will not be listed, only the derived information for each derived score will be listed.

Open-label Extension:

Descriptive summaries described above for the blinded phase will be repeated for OLE visits.

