#### **Blinded Phase:**

The number of patient responders (including the key secondary endpoint) and the number of patients seizure-free will be summarized and analyzed using a Cochran–Mantel–Haenszel test stratified by age group. In addition, the difference in proportions and the odds ratio, together with 95% CIs, comparing the treatment groups will be presented.

For number of seizure-free days, use of rescue medication, number of episodes of *status epilepticus* (only if there is a sufficient number of patients with data), Vineland-II, Wechsler scales, CBCL, ABCL, SCQ, QOLCE and QOLIE-31-P scores, the data will be summarized at baseline and over the treatment period, and at each time-point (or 28-day period, as appropriate) during the maintenance period. Changes from baseline to the average over the treatment period (or at end of study) will be analyzed using ANCOVA (or appropriate non-parametric methods if data are found to be not normally distributed). The models will include baseline and age group as covariates and treatment group as fixed factor. The treatment difference, together with the 95% CIs will be presented.

The changes in composite focal seizure score, change in total seizures, the number of seizures by subtype and the number of 'other' seizures will be analyzed using the same analysis as the primary endpoint.

SGIC-SD/CGIC-SD, SGIC/CGIC and PGIC assessments recorded at the end of treatment will be analyzed with ordinal logistic regression using the proportional odds model.

Changes from baseline for IGF-1 levels will be summarized by treatment group and plotted against the Tanner Stages, weight, and height.

Tanner Stages will be evaluated and summarized descriptively at each time-point in terms of frequency and proportions. Number (%) of patients with changes in Tanner Stages will be summarized by treatment group.

In order to explore the robustness of the primary analysis, further sensitivity analysis (in addition to that already detailed in Section 13.6.2.1) may be specified in the SAP.

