5.5 Efficacy Analysis

5.5.1 General Approach

Blinded Phase:

The primary analyses will use the ITT analysis set. Further analyses using the PP analysis set will also be performed for the primary endpoint and secondary endpoints where specified in the sections below.

The primary null hypothesis is:

- Following 16 weeks of treatment there is no difference in effect between the 25 mg/kg/day GWP42003-P treatment arm and the placebo treatment arm in terms of the change in number of TSC-associated seizures during the treatment period compared to baseline.

The null hypothesis will be rejected if there is statistical evidence of a difference between the treatment arms at the α -level of 0.05 for the primary endpoint.

Statistical hypothesis testing will be performed on the primary endpoint and other endpoints as appropriate. Each endpoint, including the primary will have 2 comparisons against placebo (25 mg/kg/day GWP42003-P vs. placebo and 50 mg/kg/day GWP42003-P vs. placebo). Also, 3 key secondary endpoints have been defined.

The primary and key secondary endpoints will be tested with their Type I error controlled by use of a hierarchical gate-keeping procedure, in the sequence given in Table 3. One must reject the null hypothesis of an endpoint at the level of 0.05 (2-sided) to test the hypothesis of the subsequent endpoint in the sequence at the level of 0.05 (2-sided). If a null hypothesis is not rejected then testing will stop and all subsequent analyses will be declared not statistically significant.

Table 3 Hierarchy for Analysis

Test	Endpoint	Treatment Comparison
1	Primary endpoint	25 mg/kg/day GWP42003-P vs. Placebo
2	1 st key secondary endpoint	25 mg/kg/day GWP42003-P vs. Placebo
3	Primary endpoint	50 mg/kg/day GWP42003-P vs. Placebo
4	1 st key secondary endpoint	50 mg/kg/day GWP42003-P vs. Placebo
5	2 nd key secondary endpoint	25 mg/kg/day GWP42003-P vs. Placebo

6	3 rd key secondary endpoint	25 mg/kg/day GWP42003-P vs. Placebo
7	2 nd key secondary endpoint	50 mg/kg/day GWP42003-P vs. Placebo
8	3 rd key secondary endpoint	50 mg/kg/day GWP42003-P vs. Placebo

All statistical tests will be 2-sided and use the 5% significance level.

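### Sex enters each SCQ model only if it is significant, so the covariate set is chosen from the outcome data and departs, unrecorded, from the protocol

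*SAP*

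**What the plan says.** SAP 5.5.4.9 defines four SCQ scores, a total and three domains. On the analysis it says "The change from baseline for each score will be analyzed using an ANCOVA approach", with a fixed part: "The model will include baseline and stratified age group as covariates and treatment arm as fixed factor". It then adds the rule at issue: "Sex will also be included as a covariate in the model only if the p-value of the estimate is <0.05". From the resulting model, "The estimated least squares means, treatment difference, together with the 95% CIs and p-value will be presented". No companion analysis from the other model is planned. The SAP does not say which fit supplies the p-value for sex.

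The questionnaire is completed "for all patients above the age of 4 years with a mental age of at least 2 years", so the analysed set is smaller than the ITT set by an amount that the documents do not give.

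Protocol 13.6.3 (blinded phase) lists SCQ among its ANCOVA endpoints and says "The models will include baseline and age group as covariates and treatment group as fixed factor". Sex is not mentioned there, and SAP 5.8, which lists changes to the planned analysis, is silent on it. SCQ is an exploratory endpoint (SAP 3.3.3) and is not in the eight-step hierarchy of SAP 5.5.1. The general rules still apply: "All statistical tests will be 2-sided and use the 5% significance level" and "Each endpoint, including the primary will have 2 comparisons against placebo".

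**The concern.** Sex is kept or dropped by a significance test on the same SCQ changes that are used to compare treatments. The model contains treatment arm, so in practice it can be fitted only after unblinding. That is an inference: the SAP does not say so, but the blinded data review meeting (SAP section 4) is given no such task.

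Two things follow. First, the test is repeated for each score, so the total may be adjusted for sex while one of its components is not, and their treatment differences are then not on the same footing. Second, the analysis departs from the protocol model without being listed as a change.

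No other ANCOVA in the SAP selects a covariate by its p-value. Seizure-free days, QOLCE, QOLIE-31-P, rescue medication, Vineland-II, Wechsler and CBCL/ABCL all have a fixed covariate set. Sex is recorded at Visit 1 (Protocol 9.2.3), so nothing forces its use to be conditional. What is at stake is a reproducible and uniform model, not error control.

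**Working it through.** **1. The plan's own figure.** The documents give no sample size, effect or SD for SCQ. Their only power figure is 90% with 70 per arm for the primary endpoint (difference 50 − 15 = 35 points, SD 60, two-sided 5%, Wilcoxon test). Noether's formula reproduces it:
- p = Φ(35/(60√2)) = Φ(0.4125) = 0.660
- N = (1.960 + 1.282)²/(3 × 0.160²) = 10.51/0.0768 = 136.8, or 68.4 per arm, so 69
- power at 70 per arm: 90.6%

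Seventy per arm is thus the planned ceiling for SCQ. I assume 35 to 70 per arm.

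**2. Overlap of the scores.** By the item lists in SAP 5.5.4.9, the domains hold 15, 13 and 8 items. That is 36 of the 39 scored items, so the total and its domains are largely the same data.

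**3. Chance of unequal models when sex has no effect.** Each test admits sex in 5% of trials. If the four scores were independent, at least one would do so in 1 − 0.95⁴ = 18.5% of trials. The scores overlap, so the true figure is probably lower.

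**4. Simulation of the rule.** Three equal arms, baseline, four age groups, residual SD 1, sex split evenly, no treatment effect, 10,000 trials per row (Monte Carlo SE about 0.2 percentage points for the type I errors). The sex effect is an assumption. Type I error is for one dose against placebo. The last two columns give the share of trials in which the verdict at 0.05 differs.

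| Per arm | Sex effect (SD) | Sex selected | Type I: rule | Type I: sex always in | Type I: sex never in | Rule v always | Rule v never |
|---|---|---|---|---|---|---|---|
| 70 | 0 | 4.7% | 5.13% | 5.03% | 5.12% | 0.52% | 0.03% |
| 70 | 0.3 | 56.4% | 5.05% | 4.90% | 5.01% | 0.33% | 1.04% |
| 70 | 0.5 | 94.3% | 5.13% | 5.08% | 5.16% | 0.07% | 2.25% |
| 35 | 0 | 5.0% | 5.15% | 5.05% | 5.11% | 0.68% | 0.08% |
| 35 | 0.3 | 31.7% | 5.42% | 5.30% | 5.25% | 0.68% | 0.73% |
| 35 | 0.5 | 68.0% | 4.74% | 4.60% | 4.46% | 0.36% | 1.58% |

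**5. With a treatment effect.** At 0.5 SD and 70 per arm (8,000 trials), rule and always differ in 0.96%, 0.75% and 0.16% of trials for sex effects of 0, 0.3 and 0.5 SD. With 35 to 60 per arm and a treatment effect near 0.3 SD, the largest figure is about 1.7%. Disagreement peaks when power is near one half: a check at 35 per arm and 0.5 SD (power about 53%) gave about 2.5%, the highest found.

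**6. Estimate and precision, rule against always (35 to 60 per arm).** The treatment estimate moves by more than 0.2 SE in about 1% to 7% of trials. The average reported SE differs by well under 1%. When sex is prognostic, the true sampling SD under the rule is about 0.2% to 0.7% larger than with sex always included.

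**The case against.** The strongest reply is that the rule is written down in advance and leaves the analyst no choice, that SCQ is exploratory, and that the error rate is nominal. All of that stands, and it limits the weight of the point.

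A reader might infer more, in three ways that the documents do not support.

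- **Type I error is inflated.** It is not. The simulated range in the table is 4.7% to 5.4%, indistinguishable from the two fixed models.
- **The rule shifts the treatment estimate noticeably or throws away precision.** That impression comes from comparing a model with sex to one without. Those two disagree at 0.05 in up to 5.9% of trials (treatment effect 0.5 SD, 70 per arm, sex effect 0.5 SD). But replacing the rule by always including sex is a different comparison. Whenever sex is selected, the two are identical. When it is not, its estimated effect is small and they nearly agree.
- **Inclusion is a coin toss.** This holds only for particular inputs. Selection runs from about 5% to 94% in the table, and no document gives a sex effect on SCQ change. Baseline SCQ is already in the model and absorbs much of any stable sex difference in level.

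It is also fair to say that including sex is not the only cure. Leaving it out fixes the model just as well and agrees with the protocol.

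**Conclusion.** The point holds as a cheap improvement to one exploratory analysis. The covariate set for each SCQ score depends on that score's outcome, overlapping scores can end up with different models, and the departure from Protocol 13.6.3 is not recorded in SAP 5.8.

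The consequence is small. Type I error stays near 5%. Against always including sex, the verdict at 0.05 changes in under 1% of trials with no treatment effect, and in roughly 1% to 2.5% at most with one. There is no meaningful difference in the reported standard error. No confirmatory result is touched. These sizes rest on assumed arm sizes (35 to 70) and an assumed sex effect of 0 to 0.5 SD. The defect itself needs no assumption, because it can be read from the text.

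**What to change.** Before unblinding, delete the conditional sentence in SAP 5.5.4.9 and state one model for the total and all three domain scores. Either form is acceptable:

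- **Include sex in all four models** and list the departure from the protocol model in SAP 5.8. The cost is one sentence, one line in 5.8 and one residual degree of freedom. With three arms of 35, a model with intercept, two treatment terms, baseline and three age terms leaves 105 − 7 = 98, which becomes 97.
- **Omit sex in all four models**, as the protocol does. The cost is one deleted sentence. If sex is strongly prognostic, some power is lost: at 70 per arm, with treatment and sex effects both 0.5 SD, simulated power is 79.8% without sex and 82.2% with it.

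The other model may be shown as a sensitivity analysis. Neither choice needs new data or alters the testing hierarchy.
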